10.4 Accrual

Maximum target sample size is estimated at 83 eligible participants which adjusts for a 15% lost to follow-up/dropout rate. In 2018 and 2017, 70 and 78 patients, respectively, met the basic inclusion criteria at UVA. Assuming 60% of future patients will agree to enroll in the study, target accrual to the study should be achieved in less than two years.

10.5 Statistical Analyses

10.5.1 Analysis populations

- a) Safety: All study participants who start protocol defined pre-ET.
- b) Primary objective: All eligible study participants who start protocol defined pre-ET for which there is an answer to both the on-study and pre-op radiation question. A participant is considered 'eligible' if she satisfies all inclusion and exclusion criteria.
- c) Secondary objective for adherence: All eligible study participants who start protocol defined pre-ET and who provide PRO measures at on-study and have information on post-op adherence to endocrine therapy.
- d) Secondary objective for radiation oncologist's preference: The subset of eligible study participants who start protocol defined pre-ET for which there is an answer to both the on-study and pre-op radiation question from a radiation oncologist.

10.5.2 Analyses

Primary analyses will not adjust for center. Summary measures will be described overall and by center. Demographics and baseline characteristics will be described for all study participants. Characteristics to be examined include: race/ethnicity, age, performance status, stage, ER, PR and HER-2 status, histologic subtype, tumor size date of diagnosis.

Adverse events will be coded based upon the NCI CTCAE v5.0. Safety will be reported by frequency and severity of adverse events.

The primary analysis will be based upon responses from a) study participants and b) surgical oncologists to the radiation questions, separately, without adjustment for center. For each response group, the proportion of responses that differ from the pre-op visit compared to the on-study (baseline) response (yes to no; or no to yes) will be calculated along with 95% confidence intervals. For each group, we will test that pre-ET resulted in a change in preference for adjuvant

Pre-Operative Window of Adjuvant Endocrine Therapy to Inform Radiation Therapy Decisions in Older Women with Early-Stage Breast Cancer

Version Date: 21 February 2023

radiation therapy in more than 10% of participants compared to no change with a one-sided 5% level exact binomial test.

Graphical methods will be used to display the PRO outcomes over time. On the most basic level, logistic regression models with adherence to post-op endocrine therapy at 2 years as the dependent outcome and the range of PRO measurement as independent factors will be used to obtain initial estimates of the predictive value of the protocol defined PRO to determine adherence. Other exploratory repeated measures models will be explored to determine if changes over time are also associated with determination of non-adherence. Exploratory analyses could include the assessment of PRO for quality adjusted life years or healthy-year equivalents. In all exploratory models, individual or simultaneous associations will be deemed promising for factors with $p < 0.1$.

The secondary analysis related to the radiation oncologist's preference will be based upon the subset of pre and post pre-ET responses from for the consulting radiation oncologist. The proportion of responses that differ from the pre-op visit compared to the on-study (baseline) response by at least one point (in either direction) will be calculated along with a 95% confidence interval.

Descriptive summaries and simple tabulations will be used to describe results from the preliminary data on justification of participant response for those whose preference changed.

At final analysis the Product-Limit method of Kaplan & Meier will be used to estimate recurrence-free survival and overall survival, along with 90% CIs. Recurrence-free survival is defined as the time from start of pre-ET to time of recurrence or death from any cause, whichever occurred first. Participants who do not experience an event (recurrence or death) will be censored at date of last clinical assessment. Overall survival is defined as the time from start of pre-ET to time of death from any cause. Participants who do not experience an event (death) will be censored at date of last contact.

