10.2 Endpoints, Statistical Hypotheses and Estimation

Assessment of the primary study objectives will be based upon answers to the radiation preference question for study participants and surgical oncologists separately. Change in preference is measured as a binary variable (yes/no) with a coding of 'yes' if answers between the pre-op and on-study (baseline) response differ (no to yes; or yes to no). No difference in response is coded as 'no'.

Hypothesis test 1: To determine if pre-treatment with endocrine therapy changes participant preference for adjuvant radiation treatment in the participant study population by at least 10% with a one-sided binomial test.

Hypothesis test 2: To determine if pre-treatment with endocrine therapy changes surgical oncologist preference for participant specific adjuvant radiation treatment in the participant study population by at least 10% with a one-sided binomial test.

Estimation: To estimate the association of pre-treatment PRO measures on the probability of long-term adjuvant endocrine therapy adherence.

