10.3 Sample Size Determination

Sample size estimation is based upon accruing a sufficient number of participants to assess the primary objective separately for participants and surgical oncologist responses with an overall one-sided 10% type I error rate (5% for each individual test). Accrual of 70 evaluable participants provides 90% power to test for a change in adjuvant radiation treatment preference between the pre-op visit and on-study in the participant study population from a null difference of 5% to an alternative of at least 15% with a target one-sided 5% level binomial test (by exact enumeration). Accrual of 70 evaluable participants also provides 90% power to independently test for a change

Pre-Operative Window of Adjuvant Endocrine Therapy to Inform Radiation Therapy Decisions in Older Women with Early-Stage Breast Cancer

Version Date: 21 February 2023

in adjuvant radiation treatment preference of the surgical oncologist between the pre-op visit and on-study in the participant study population from a null difference of 5% to an alternative of at least 15% with a one-sided 5% level binomial test. For fixed target size and power, the detectable difference increases from 10% to 15% when the assumed null varies within the expected range of 5% to 20%.

This is a pilot study to obtain preliminary data to estimate which if any PRO measures are associated with adherence to post-operative endocrine therapy. With n=70, a logistic regression of the dependent variable of adherence or not to endocrine therapy by year 2 on a continuous PRO measure score achieves 80% power at a 5% significance level to detect an odds ratio of 2 when the probability of adherence is 25%. These error rate estimates assume no adjustment for multiple comparisons among the different PRO.

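### The two primary tests have no single stated null (5% or 10%), and the two versions give opposite verdicts for 8 to 11 changers out of 70

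*Combined protocol and SAP*

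**What the plan says.** Three sections describe the primary tests, which are run separately for participants and for surgical oncologists.

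- **Section 10.3** (sample size): 70 evaluable participants give 90% power for a shift "from a null difference of 5% to an alternative of at least 15% with a target one-sided 5% level binomial test". The level is one-sided 5% per test and 10% overall. The section adds that, at fixed size and power, "the detectable difference increases from 10% to 15% when the assumed null varies within the expected range of 5% to 20" percent.
- **Section 10.2** (hypotheses): the participant test asks whether preference changes "in the participant study population by at least 10% with a one-sided binomial test". The surgical oncologist test uses the same threshold. No null is given.
- **Section 10.5.2** (analysis): for each group the test is of a change in preference for adjuvant "radiation therapy in more than 10% of participants compared to no change with a one-sided 5% level exact binomial test".

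No section says that 5% is the null for the analysis, and none reconciles 5% with 10%.

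**The concern.** An exact binomial test needs one null rate. Section 10.3 writes 5%. Section 10.5.2, the text that governs the analysis, describes a proportion of participants above 10%, which as a test means H0: p ≤ 10%. Its closing reference to no change does not help: as a null of 0%, a single changer would reject.

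Both primary verdicts depend on the choice. The study is open-label with no masking, so settling the null once the number of changers is known would be a post hoc decision. Two errors are possible. If the 5% null is used but the result is reported in the words of 10.5.2, a claim of more than 10% may be made when it is not supported. If the literal 10% null is used, the trial has far less power at 15% than 10.3 states.

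There is also a smaller mismatch. Even if 5% is intended, the 90% power in 10.3 and the 5% level exact test in 10.5.2 do not correspond to the same cutoff.

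**Working it through.** **Inputs.** n = 70 evaluable, null 5%, alternative 15%, one-sided 5% per test (10.3); 10% threshold (10.2, 10.5.2); exact binomial test (10.5.2); maximum of 83 participants (10.4). X is the number of changers, X ~ Binomial(n, p). Size is P(X ≥ r | null rate) and power is P(X ≥ r | true rate).

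**Reproducing the stated 90% power (null 5%, alternative 15%, n = 70).**

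| Rule | Size | Power at 15% |
|---|---|---|
| X ≥ 7 (size nearest 5%) | 0.0604 | 0.916 |
| X ≥ 8 (size strictly ≤ 5%) | 0.0234 | 0.843 |
| Normal approximation | nominal 0.05 | 0.910 |

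The 90% is reproduced with X ≥ 7 or the normal approximation, but not with a strict exact test. At 7/70 the exact p-value is 0.060, so a strict 5% exact test does not reject there.

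The nearest-to-target rule also matches the detectable differences in 10.3. With a 5% null (X ≥ 7), 90% power is reached at a true rate of 14.6%, a gap of 9.6 points. With a 20% null (X ≥ 20, size 0.0545) it is reached at 35.1%, a gap of 15.1 points. The strict rule gives 11.2 and 16.6 points. Two tests at 6.04% each have an overall error of at most 2 × 0.0604 = 12.1%, against the stated 10%.

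**The literal 10% null (n = 70).** X ≥ 12 has size 0.0441. Power is 0.356 at 15%, 0.768 at 20% and 0.956 at 25%. Power of 90% is reached at a true rate of about 22.8%, a gap of 12.8 points.

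**Where the verdicts part (exact one-sided p-values, n = 70).**

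| Changers | Observed rate | p, null 5% | p, null 10% |
|---|---|---|---|
| 7 | 10.0% | 0.060 | 0.558 |
| 8 | 11.4% | 0.023 | 0.401 |
| 9 | 12.9% | 0.008 | 0.264 |
| 10 | 14.3% | 0.002 | 0.159 |
| 11 | 15.7% | 0.0007 | 0.087 |
| 12 | 17.1% | 0.0002 | 0.044 |

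With strict tests the disputed counts are 8 to 11. If X ≥ 7 is used for the 5% null, they are 7 to 11.

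**Chance of a disputed result, P(8 ≤ X ≤ 11), by true rate.**

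| True rate | 5% | 10% | 15% | 20% | 25% | 30% |
|---|---|---|---|---|---|---|
| Probability | 2% | 36% | 49% | 21% | 4% | 0.5% |

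At 15%, P(7 ≤ X ≤ 11) = 56%.

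**Mixing the versions.** If X ≥ 8 is the rule but the claim is a rate above 10%, then at a true rate of exactly 10% the claim is made with probability P(X ≥ 8 | 0.10) = 0.401.

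**Confidence intervals (Clopper-Pearson 95%).** 8/70: 5.1% to 21.3%. 11/70: 8.1% to 26.4%. Across the disputed range the interval excludes 5% and includes 10%.

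**If all 83 were evaluable.** Null 5%: X ≥ 9, size 0.023, power 89.2% at 15%. Null 10%: X ≥ 14, size 0.035, power 36.1% at 15%. The disputed counts become 9 to 13.

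**The case against.** A consistent reading can be offered. Section 10.3 is the only place that writes both a null and an alternative, and it calls the 10-point gap a detectable difference. The 10% in 10.2 could be that gap, and 10.5.2 could be loose shorthand for it. This reading may fit 10.2. It does not fit 10.5.2, which states a proportion of participants, so that text needs rewording in any case.

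A 10% null also lies within the 5% to 20% range in 10.3, and its 12.8-point detectable difference fits the 10-to-15-point statement there. That is correct, and 10.3 claims 90% power at 15% only for the 5% null. But a range of nulls does not say which one the analysis uses.

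The choice between 7 and 8 is a matter of discreteness. Section 10.3 speaks of a target level, and a mid-p version of the test would reject at 7/70 (p = 0.042). The 12.1% is an upper bound; independence of the two tests would give 11.7%, and positive correlation less. This strand is secondary, but the plan names an exact test at the 5% level and should give the cutoff it means.

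Finally, this is a pilot, no go/no-go rule hangs on the p-value, and 95% intervals will be reported, so readers can see the range. The chance of a disputed result is also close to its highest at 15% and small above 25%. All of that tempers the consequence. The plan still prespecifies two tests with an error rate and power, and the intervals for 8 to 11 changers do not settle which verdict is reported.

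**Conclusion.** The concern holds. The plan does not fix the null for either primary test, and the conflict is in its current text. At n = 70 with strict exact tests, 8 to 11 changers give opposite verdicts, with probability 49% at the design alternative of 15% and 36% at a true rate of 10%. Depending on the null, power at 15% is 84% or 36%. The stated 90% is reached only with a cutoff whose actual size is 6.0%, or by normal approximation.

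These figures assume 70 evaluable participants, independent binary responses with a common change rate, and the literal reading of 10.5.2 as a 10% null. The disputed counts shift with the evaluable number, but the conflict remains. It should be corrected before the primary analysis because it determines both primary conclusions.

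**What to change.** State one null and one rejection count in 10.2, 10.3 and 10.5.2, with the rule for evaluable numbers other than 70. The choice belongs to the sponsor:

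- **(a) Null 5% throughout.** Reject at 8 or more of 70, restate power in 10.3 as 84% at 15% (90% at about 16.2%), and conclude only that more than 5% changed. This is the smaller departure from the plan, since 5% is the only null written out. A cutoff of 7 with about 92% power could be kept instead if the 6.0% size per test and the overall error of up to 12.1% are disclosed.
- **(b) Null 10% throughout.** Reject at 12 or more of 70, and restate power as 36% at 15% and 90% at about 23%. This supports a claim of more than 10%.

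In either case, clarify or delete the reference to no change in 10.5.2.

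The cost is wording in three sections and a restated power figure, with no added participants. Under (a) the claim narrows to more than 5% and the stated power falls, or the larger size is disclosed. Under (b) the plan must acknowledge low power at 15%.

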1 PROTOCOL SUMMARY

1.1 Synopsis

Title:	Pre-Operative Window of Adjuvant Endocrine Therapy to Inform Radiation Therapy Decisions in Older Women with Early-Stage Breast Cancer	
Study Description:	
This is a prospective multisite exploratory study for women ≥ 65 years of age with early stage estrogen receptor positive (ER$^+$) breast cancer. These individuals will be treated with 3 months of pre-operative endocrine therapy (pre-ET) with assessment of tolerance to the endocrine therapy by patient reported outcome (PRO) measures. The results of this study will be used to develop an algorithm for treatment recommendations in early stage geriatric breast cancer patients.
 
The following will be assessed:
 
1) The results of the tolerance assessments will change the treatment recommendations and decisions regarding adjuvant radiation therapy (RT);2) Tolerance of pre-ET as measured by PROs will be predictive of long-term adjuvant endocrine therapy adherence;3) Use of 3 months of pre-ET endocrine therapy in order to assess tolerance to the endocrine therapy will not negatively impact surgical completion.	
Objectives & Endpoints	Objectives	Endpoints
	Primary	
• Radiation preference question for participant pre and post pre-ET treatment• Radiation preference question for the surgical oncologist pre and post pre-ET treatment
	Secondary	
• PRO assessments• Radiation preference question for the radiation oncologist pre and post pre-ET treatment
	
• To obtain preliminary data on the effect of pre-ET on decision outcomes for adjuvant therapy after BCS	
• PRO assessments
	Exploratory	

Pre-Operative Window of Adjuvant Endocrine Therapy to Inform Radiation Therapy Decisions in
Older Women with Early-Stage Breast Cancer

Version Date: 21 February 2023

[figure not shown]
	
• To obtain exploratory data on recurrence-free survival and overall survival• Recurrence-free survival and survival through 24 months	
Study Population:	Women ≥ 65 years of age with a diagnosis of clinical stage I, ER ⁺ , progesterone positive (PR ⁺) or negative (PR ⁻), and HER2 non-amplified invasive breast cancer and clinically negative nodes. Any invasive breast cancer histologic subtype may be enrolled.	
Phase:	Pilot study	

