The ELPh trial reported on PROs and examined whether early changes in PROs predict AI discontinuation. In this study, health-related quality of life (HRQoL) was assessed using the EuroQOL Visual Analog Scale (EuroQOL VAS), depression was assessed using the Center for Epidemiologic Studies-Depression (CESD) tool, anxiety was assessed with the anxiety subscale of the Hospital Anxiety and Depression Scale (HADS), and symptom burden was assessed using the Breast Cancer Prevention Trial Symptom Checklist (BCPT-SCL). The BCPT-SCL was analyzed by symptom clusters of weight/body image, vasomotor, vulvovaginal, musculoskeletal,

Pre-Operative Window of Adjuvant Endocrine Therapy to Inform Radiation Therapy Decisions in Older Women with Early-Stage Breast Cancer

Version Date: 21 February 2023

cognitive, and mood. The PROs were assessed at regular intervals on adjuvant AI therapy. The musculoskeletal symptom burden assessment was noted to be rising at month 1 and significantly higher by month 3 and month 6 ($p = 0.023$, $p = 0.033$). Of the examined PROs, rising musculoskeletal scores and decreasing HRQOL scores were found to predict discontinuation of AI³³. This study demonstrates that side effects develop early in patients on AIs and are predictive of early discontinuation and non-adherence. In the present study, we plan to assess if this can be looked at in a brief course of pre-ET to predict long term tolerance and adherence of adjuvant endocrine therapy.

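### Section 10.5.2 allows PRO scores to be entered jointly against about 17 women in the smaller outcome class, with no limit and no optimism correction, so the reported predictive value could look useful when nothing predicts

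*Combined protocol and SAP*

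**What the plan says.** Section 10.3 presents the PRO aim as preliminary: "This is a pilot study to obtain preliminary data to estimate which if any PRO measures are associated with adherence to post-operative endocrine therapy". Its sizing statement concerns one score: "With n=70, a logistic regression of the dependent variable of adherence or not to endocrine therapy by year 2 on a continuous PRO measure score". For that model it claims 80% power at the 5% level for an odds ratio of 2, taking adherence to be 25%. It adds: "These error rate estimates assume no adjustment for multiple comparisons among the different PRO".

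Section 10.5.2 is wider. It plans logistic models, in the plural, in which "the range of PRO measurement as independent factors will be used to obtain initial estimates of the predictive value". It then says that "individual or simultaneous associations will be deemed promising for factors with" p < 0.1.

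Neither section says which or how many PRO scores may enter one model, which time point supplies them, or how predictive value is measured. Neither mentions penalisation, internal validation or a correction for optimism.

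The instruments are named in sections 4.1 and 8.2.3: QLQ-C30, QLQ-BR23, BCPT-SCL (to be followed as six symptom clusters) and CESD-R. Section 3 lists prediction of long-term adherence from PROs as a secondary objective. The synopsis says that the study's results "will be used to develop an algorithm for treatment recommendations".

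**The concern.** A logistic model fitted to few events with many predictors discriminates well on its own data even when the predictors are noise. Judging the model on the women used to fit it then overstates how well PROs separate those who will stay on endocrine therapy from those who will not. The exploratory label excuses the lack of error control. It does not remove an upward bias from an estimate. At stake is a listed secondary objective in a study whose results are meant to inform later treatment recommendations.

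**Working it through.** **Inputs.** From section 10.3: n = 70, probability of adherence 0.25, odds ratio 2, 5% level, 80% power, one continuous score. From sections 4.1 and 8.2.3: six BCPT-SCL clusters, one CESD-R score, and the EORTC questionnaires (53 items, number of scale scores not given). Assumed: one or two EORTC scores; AUC as the measure of predictive value; ordinary unpenalised logistic regression.

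**The plan's own figure.** For one standardised covariate, N = (z_alpha + z_power)^2 / [p(1 - p) x (ln OR)^2].
- Denominator: 0.25 x 0.75 x 0.6931^2 = 0.1875 x 0.4805 = 0.0901.
- One-sided 5%: (1.645 + 0.842)^2 / 0.0901 = 68.6, and power at n = 70 is 80.7%. The stated 80% is reproduced.
- Two-sided 5%: (1.960 + 0.842)^2 / 0.0901 = 87.1, and power at n = 70 is 70.9%.

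So the sizing holds for a single PRO with a one-sided test. Section 10.3 does not state the sidedness.

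**Events per score.** The smaller class has 70 x 0.25 = 17.5 women. The smallest count with the BCPT-SCL clusters kept separate is 6 + 1 + 1 = 8, or 6 + 1 + 2 = 9. That gives 17.5/8 = 2.2 or 17.5/9 = 1.9 women per score. With four whole-instrument scores it is 17.5/4 = 4.4.

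**Apparent AUC when no PRO predicts.** Simulation with n = 70, 17 or 18 events, normally distributed scores with pairwise correlation 0 or 0.5, all entered together, and at least 600 runs per setting. The true AUC is 0.50.

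| Scores in one model | Median apparent AUC | Runs reaching 0.70 |
|---|---|---|
| 1 | 0.55–0.56 | rare |
| 4 | 0.64–0.65 | 16–19% |
| 8 | 0.71–0.72 | 58–63% |
| 9 | 0.73 | 71% |
| 15 (assumed) | 0.80–0.81 | 97–98% |

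**Sensitivity to the event count, 8 scores.** The median is 0.80 with 7 events, 0.74–0.75 with 12, 0.70 with 23 and 0.69 with 35. The background figures in section 2.2.4 give 70 x 0.05 = 3.5 to 70 x 0.25 = 17.5 discontinuing within two years, or 70 x 0.326 = 22.8 on the AI trial's rate. The inflation therefore does not depend on the 25% assumption.

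**Chance that at least one null PRO is called promising (p < 0.1).**
- Tested singly: 30–32% with 4 scores, 44–57% with 8, 58–79% with 15. The lower ends are for correlated scores. For independent scores the formula gives 1 - 0.9^8 = 57%, matching the upper end at 8.
- Entered jointly: 33–35% with 4, 57–59% with 8, 64–66% with 9.

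**Effect of bootstrap correction.** The mean null AUC falls from 0.64 to 0.54 with 4 scores, and from about 0.71–0.73 to about 0.57–0.58 with 8 or 9. With 15 it stays above 0.60.

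**The case against.** The strongest reply is that the plan does not commit to a joint model. It speaks of models in the plural, allows individual associations, and is sized on one PRO. Fitted that way, the null apparent AUC is about 0.55 and the overfitting does not arise. That stands, and it limits the point to the simultaneous models that the text also permits. The number of scores is open too: with four whole-instrument scores, reaching 0.70 by chance is unlikely.

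The plan also discloses that it makes no multiplicity adjustment, uses only the word promising, and calls the aim preliminary. That answers a complaint about error control. It does not answer inflation in an estimate of predictive value.

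Three stronger readings are tempting and are not supported:
- A reader might infer that the predictive value is bound to look good, by a known amount. The size depends on a score count and a performance measure that the plan leaves open.
- A reader might infer from the synopsis that inflated performance would pass straight into a decision tool. Section 2.3 describes that tool as a later intention that would add demographic and histopathologic factors.
- A reader might take the protocol's own background as supplying a two-predictor lead model, since in the cited trial "rising musculoskeletal scores and decreasing HRQOL scores were found to predict discontinuation of AI". That trial studied AIs only and measured HRQOL with the EuroQOL VAS. This study also allows tamoxifen and uses the EORTC questionnaires. Change scores need on-treatment PROs, whereas the adherence population in section 10.5.1(c) requires PROs only at on-study.

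**Conclusion.** The concern holds for simultaneous models. If the 8 or 9 scores enter together and none predicts adherence, the apparent AUC would more likely than not reach 0.70. At 15 scores this is nearly certain; at 4 or fewer it is unlikely. With one PRO per model what remains is selection: about a 44 to 57% chance that at least one of 8 null scores is called promising.

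These figures rest on AUC as the measure, one or two EORTC scores, unpenalised fitting, 70 women with 2-year data and 25% in the smaller class. This is more than missing detail, because an analysis the plan allows gives a materially inflated estimate for a secondary objective and a better method is readily available. The change should be made, but it does not touch the primary analysis.

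**What to change.** In section 10.5.2:
1. Make single-PRO logistic models the main adherence analysis. They match the sizing in section 10.3.
2. Fit any simultaneous model with penalised logistic regression (ridge or Firth). Penalisation stabilises the coefficients but does not by itself make the apparent discrimination honest, so step 3 is still needed.
3. Name the performance measure, and report bootstrap optimism-corrected discrimination beside or instead of the apparent value. Repeat any variable selection inside each bootstrap sample.
4. State how many PRO scores were tested next to any called promising.

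The cost is plan wording and a little programming, with no new participants, visits or data. The reported predictive value will be lower. The bootstrap removes most of the optimism but not all of it: about 0.57 to 0.58 remains with 8 or 9 null scores. That is a reason to keep joint models small.
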